Cover Page

**A Randomized Controlled Trial to Evaluate Botulinum Toxin A alone versus Botulinum
Toxin A with hydrodistention for the Treatment of Refractory Overactive Bladder
(HydrA Study)**

NCT02995967

Research Protocol

A Randomized Controlled Trial to Evaluate Botulinum Toxin A alone versus Botulinum Toxin A with hydrodistention for the Treatment of Refractory Overactive Bladder (HydrA Study)

[name], MD¹

[name], MD¹

[name], MD²

[name], MD²

[name], MD¹

[name], MD¹

[name], MD¹

1. Division of Urogynecology and Pelvic Reconstructive Surgery, Department of Obstetrics and Gynecology, University of Alabama Birmingham, Birmingham, AL
2. Department of Urology, University of Alabama Birmingham, Birmingham, AL

Corresponding Author:

[name]

[name]

[name]

[contact]

[contact]

Email: [contact]

FINANCIAL DISCLAIMER/CONFLICT OF INTEREST: NONE

[name]: Protocol/project development, data collection, manuscript writing/editing

Abstract

The specific aim of this randomized, single-blinded controlled trial is to determine if hydrodistention at the time of intradetrusor injection of botulinum toxin A has additional benefit in patients with refractory overactive bladder (OAB) and urgency symptoms compared to intradetrusor injection of botulinum toxin A alone.

Consented patients will be randomized to hydrodistention at a pressure of 80 cm H₂O for 5 minutes, prior to the intradetrusor injection of 100 units of botulinum toxin A (hydrodistention group) or intradetrusor injection of 100 units of botulinum toxin A alone (botulinum toxin A alone group). The primary aim will be subjective improvement measured as change from baseline at 12 weeks using the OAB-q bother subscale. Secondary aims will include number of urgency urinary incontinence (UII) episodes, total number of voids, percentage of patients requiring clean intermittent self-catheterization, elevated post-void residual, health related quality of life, patient global impression of improvement, patient satisfaction, rate of urinary tract infection post-operatively, and 24 week subjective improvement using the OAB-q.

Demographics and baseline data will be analyzed by Student's t-test and chi-squared test or Fisher's Exact test as appropriate.

Specific aims

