Primary aim: To determine if hydrodistention at the time of intradetrusor injection of botulinum toxin A has additional symptomatic benefit in patients with overactive bladder (OAB) and urgency symptoms compared to botulinum toxin A injection alone in a single blind, randomized controlled trial using subjective improvement as measured by the OAB-q bother subscale at 12 weeks.

Secondary aims: Secondary aims will include number of urgency urinary incontinence (UII) episodes, total number of voids, proportion of subjects requiring clean intermittent self-catheterization, elevated post-void residual, health related quality of life, patient global impression of improvement, patient satisfaction, rate of urinary tract infection post-operatively, and 24 week subjective improvement using the OAB-q.

Null hypothesis: In subjects with refractory overactive bladder, hydrodistention at the time of intradetrusor injection of botulinum toxin A will result in no difference in OAB-q score compared to botulinum toxin A injection without hydrodistention.

Background

Overactive bladder (OAB) is a common condition that affects approximately 17% of women in the United States [1]. Overactive bladder is defined by the International Continence Society as “urinary urgency, usually accompanied by frequency and nocturia, with or without urgency urinary incontinence, in the absence of urinary tract infection or other obvious pathology” [2]. Approximately one third of these women will have urgency urinary incontinence (UII) with the prevalence increasing with age [1]. The economic burden of this disease is significant with the estimated annual cost of OAB in the United States being \$25 billion [3].

Anticholinergic medications have long been the mainstay of treatment for OAB but have significant side effects including dry mouth and constipation [4] which has led to poor patient compliance and high discontinuation rates in clinical practice [5]. Botulinum toxin A injected into the detrusor muscle during cystoscopy was Food and Drug Administration approved for the treatment of refractory OAB symptoms in 2013. This approval was based on two large randomized controlled trials that included 1,105 patients randomly assigned to placebo or 100

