1. Women with refractory overactive bladder symptoms, failing a credible behavioral therapy intervention and medical therapy or not tolerating medical therapy. Patients who are on medical therapy will stop the medical therapy for at least 2 weeks prior to botulinum toxin A treatment in the study
2. Female \geq 18 years old
3. Desires further treatment for OAB symptoms.
4. Express understanding and ability to perform clean intermittent self-catheterization (CISC) if required.
5. Ability to consent
6. Ability to complete all study related items and interviews

Exclusion Criteria

1. Post void residual urine volume > 150 mL as assessed by catheter or ultrasound
2. History of intradetrusor botulinum toxin A injection
3. History of or current cancer of the genitourinary or gynecology tract

4. Neurogenic bladder
5. Interstitial cystitis
6. Current urinary tract infection (can be treated and re-considered for study)
7. Current active sacral neuromodulation device
8. Non-English speaking
9. History of chronic pelvic pain
10. Hematuria not previously evaluated

Intervention

Hydrodistention at a pressure of 80 cm H₂O for 5 minutes prior to intradetrusor injection of 100 units of botulinum toxin A (hydrodistention group) or intradetrusor injection of 100 units of botulinum toxin A alone (botulinum toxin A alone group).

Primary outcome

The primary outcome will be measured as change from baseline at 12 weeks using the OAB-q bother subscale which consists of eight questions assessing symptom bother with a possible score from 0 to 100 with a higher score indicating greater symptom bother.

Secondary outcomes

1. Number of UUI episodes as reported in a 3-day bladder diary at 12 weeks as measured in change from baseline.
2. Total number of voids reported in the 3-day bladder diary at 12 weeks as measured in change from baseline.

3. Proportion of subjects requiring clean intermittent self-catheterization (CISC) post-operatively as reported at 2 week post-operative visit. CISC will be initiated at post-void residual volumes of > 300 mL *or* > 150 mL in the presence of bothersome retention symptoms.
4. Post-void residual volume (PVR) at the 2 week follow-up visit measured with catheter or bladder scan.

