Subjects randomized to the botulinum toxin A alone group will undergo intradetrusor injection of 100 units of botulinum toxin A diluted in 10 cc of sterile normal saline and injected in volumes of 0.5cc in a grid-like pattern using rigid cystoscopy in the operating room under monitored anesthesia care (MAC) or general anesthesia. Those subjects randomized to the hydrodistention group will undergo hydrodistention of the bladder in the operating room just prior to the botulinum toxin A injection. The hydrodistention will be performed with a water pressure of 80 cm H₂O as measured by the height of the sterile water source above the pubic symphysis in the operative room. The bladder will be filled and noted to be full as evidenced by no further influx of water into the bladder. The bladder will be emptied and this volume will be

recorded as initial bladder volume. The hydrodistention will then be performed with the bladder filled at a pressure of 80 cm H₂O and noted to be full as evidenced by no further influx of water into the bladder. This volume will be held in the bladder for 5 minutes. Upon emptying, the volume will be recorded as the hydrodistention volume. After the hydrodistention, these subjects will then receive intradetrusor injection of 100 units of botulinum toxin A in a grid like pattern using rigid cystoscopy as described above.

Subjects will be seen for a 2 week post-operative visit. It will be recorded if subjects have had to use CISC including how many days. CISC will be initiated at post-void residual volumes of > 300 mL *or* > 150 mL in the presence of bothersome retention symptoms. Subjects with symptoms of UTI including dysuria, urgency, frequency, temperature \geq 38 degrees Celsius and/or suprapubic pain will have urine culture sent and treated accordingly for UTI. If subjects call with symptoms of urinary tract infection but are unable to present for urine culture will also be treated and reported as an UTI.

Subjects will follow up for scheduled post-operative care at a 6 and 12 weeks at which time they will complete the OAB-q, PGI-I, and PSQ for the 12 week primary outcome data. Subjects will complete a 3 day bladder diary during the week prior to the 12 week visit and bring the information with them to the visit. At the 24 week follow up visit, patients will complete the OAB-q. All follow up visits at 2 weeks, 6 weeks, 12 weeks, and 24 weeks will be plus or minus a 1 week window from the date of procedure.

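### Self-catheterization begun after the 2-week visit does not enter the outcome, although benefit is followed to weeks 12 and 24

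*Combined protocol and SAP*

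**What the plan says.** Secondary outcomes, item 3, defines the outcome as the proportion of women "requiring clean intermittent self-catheterization (CISC) post-operatively as reported at 2 week post-operative visit". In Protocol in detail, the matching data collection stands in the paragraph on the 2-week visit: "It will be recorded if subjects have had to use CISC including how many days". Both places give the same start rule, with no limit in time: "CISC will be initiated at post-void residual volumes of > 300 mL", or at a lower volume when retention symptoms are bothersome.

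The later visits are described by their questionnaires. For weeks 6 and 12: "Subjects will follow up for scheduled post-operative care at a 6 and 12 weeks at which time they will complete the OAB-q", together with the global impression and satisfaction questionnaires, and a bladder diary before week 12. For week 24: "At the 24 week follow up visit, patients will complete the OAB-q". None of these lists has a CISC item. All follow-up visits "will be plus or minus a 1 week window from the date of procedure".

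The Abstract names the "percentage of patients requiring clean intermittent self-catheterization, elevated post-void residual" among the secondary aims, and Specific aims names the "proportion of subjects requiring clean intermittent self-catheterization, elevated post-void residual". Neither gives a time point for the two measures. Secondary outcomes, item 4, then places post-void residual volume (PVR) at the 2-week visit as well.

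**The concern.** CISC is an event counted from the procedure onward, so the date on which counting stops is part of its definition. Here counting stops at a visit that may take place on any day from 7 to 21. A woman who starts later does not enter the outcome, and the listed forms would not show that she had started.

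The balance of benefit and burden is therefore observed over unequal periods. Symptom scores are taken to weeks 12 and 24, and the Background section argues that added bladder capacity may be sustained for longer when distention is combined with the toxin. The catheterization burden is captured only early. By comparison, the urinary tract infection outcome has a route for women who telephone at any time in the study; CISC has none.

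There is also a small ambiguity. Item 3 speaks of women who require CISC, while the procedures record whether women have already had to use it. A woman who starts because of the PVR measured at the 2-week visit could be coded either way. As that is the only post-procedure PVR listed, the case is a foreseeable one.

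At stake is how one secondary outcome, which bears on safety, is described. The primary outcome is not touched.

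**Working it through.** **The plan's own figure.** The documents give no rate, timing or power for CISC. The only relevant figures are the arm sizes in Power analysis. A difference of 15 points with a standard deviation of 19, two-sided alpha 0.05 (sidedness assumed) and 80% power gives 26.2 per group by the two-sample t-test, rounded up to 27. Allowing for 10% dropout, 27 / 0.90 = 30 per group. Both stated figures reproduce, and they serve below only as denominators.

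**Visit windows** (nominal day plus or minus 7, Protocol in detail):

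| Visit | Nominal day | Window | CISC item listed |
|---|---|---|---|
| 2 weeks | 14 | 7 to 21 | yes |
| 6 weeks | 42 | 35 to 49 | no |
| 12 weeks | 84 | 77 to 91 | no |
| 24 weeks | 168 | 161 to 175 | no |

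**Length of the counted period.** It is nominally 14 days, and 7 to 21 days at the edges of the window. Against the 84 days to the primary time point that is 14/84 = 16.7%, with a range of 7/84 = 8.3% to 21/84 = 25.0%. The longest period over the shortest is 21/7 = 3, reached only when two women sit at opposite edges.

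**Effect of one uncounted start on an arm's proportion.**
- 1/30 = 3.3 percentage points, if all recruited women are counted.
- 1/27 = 3.7 percentage points, if 27 women complete.

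**Number of later starts.** This cannot be derived. As an assumed range, 0 to 3 per arm gives 0 to 3/30 = 10.0 points, or 0 to 3/27 = 11.1 points. A model does not help. If time to start is assumed exponential with mean m days, the share of starts captured by day 14 is 1 - exp(-14/m). That is 86% for m = 7 and 39% for m = 28. The answer follows the assumed m, for which the documents offer nothing.

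**Would a common cut-off day repair the varying window?** The earliest 6-week visit (day 35) comes 35 - 21 = 14 days after the latest 2-week visit. Start dates asked at week 6 would therefore cover day 21 in every woman who attends. This equalizes the calendar period but not detection. The start rule depends on PVR, and PVR is listed only at the 2-week visit, so a woman seen on day 7 is checked then and one seen on day 21 is checked then.

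**The case against.** The strongest reply is that this is a chosen endpoint, stated openly. Item 3 names its visit, item 4 uses the same visit, and so does the culture-based part of the infection outcome; together they form a coherent early post-operative assessment. On that view a later start lies outside the endpoint and is not a missed event. This largely stands, and it is why the 2-week proportion should be kept.

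Four stronger readings are tempting, and the documents do not support them:

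- *The aims contradict the outcome.* The aims leave out the time point for PVR too, so they are summaries.
- *A later starter is wrongly recorded as a non-user.* No sentence says so. What follows from the text is only that her start does not enter this outcome. Nor do the documents state that CISC is recorded nowhere else; the visit lists simply do not include it.
- *The window biases the comparison.* The threefold ratio is an extreme, and the same window applies to both arms. Bias would need visit dates or start dates to differ by arm. Only the women are said to be blinded, so this is possible, but nothing shows it.
- *Burden is materially understated.* The range of 0 to 3 later starts is assumed, and its lower end is no effect.

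It may also be said that several versions of one outcome in 60 women invite unplanned comparisons, since Data analysis names no test for any secondary outcome. That is fair, and it argues for keeping the additions descriptive.

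**Conclusion.** The point holds as a limitation of one secondary outcome that can be improved, not as an error. As listed, CISC is captured at a visit on day 7 to 21, and a start after that visit does not enter the outcome, while benefit is followed to weeks 12 and 24. Each such start would be worth about 3.3 to 3.7 percentage points in its arm; how many there will be is unknown from the documents. The conclusion assumes that the visit lists in Protocol in detail are complete for CISC. The sample size is unaffected. The change is worth making because the plan as listed could not show whether later starts are rare or common.

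**What to change.** 1. Keep the 2-week proportion as defined, and add one sentence that a start at that visit counts.
2. Record CISC as yes or no, with start and stop dates, at the existing 2-, 6-, 12- and 24-week visits.
3. Report by arm, descriptively, any CISC from the procedure to week 12, and list later starts to week 24.
4. Do not add a separate day-21 proportion, or give it only with the caveat that detection still depends on the date of the 2-week PVR.
5. State in the report that, with PVR listed only at the 2-week visit, later starts are those that arise in care, so the week-12 figure is a minimum.

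The cost is dates added to the 2-week form, one extra item at three visits already scheduled, and a little data entry. No visit or procedure is added, and the clinical rule for starting CISC is not changed.

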5. Rate of urinary tract infection (UTI) as assessed by positive urine culture in patients having symptoms (dysuria, urgency, frequency, temperature ≥ 38 degrees Celcius, and/or suprapubic pain) at the 2 weeks post-operative visit. Subjects who call throughout the study complaining of symptoms but are unable to give a urine culture in clinic will also be treated and reported as having had a UTI.
6. Health related quality of life (HRQL) will be measured as a change from baseline at 12 weeks using the OAB-q HRQL subscale part which consists of 25 questions that assess HRQL addressing coping, concern, sleep, and social interaction where the scoring scale is from 0 to 100 with a higher score indicating a better quality of life.
7. Patient global impression of improvement at 12 weeks as measured using the Patient Global Impression of Improvement Questionnaire (PGI-I).
8. Patient satisfaction at 12 weeks as measured using Patient Satisfaction Questionnaire (PSQ).
9. Subjective outcome at 24 weeks using the OAB-q

Protocol in detail

Women seen in the urogynecology and urology clinics at University of Alabama at Birmingham who are seeking treatment for refractory OAB symptoms will be screened. Patients

who have failed a credible behavioral therapy intervention and medical therapy or not tolerating medical therapy will be evaluated for this study. Those patients satisfying the inclusion/exclusion criteria will be offered to participate in the study. Informed consent will be reviewed and signed with patients wishing to proceed.

At enrollment, any subjects who are using medical therapy including anticholinergic or β_3 agonist medications will stop these therapies for at least 2 weeks prior to treatment. Baseline clinical data including OAB-q and a 3 day bladder diary will be collected as well as clinical and demographic information. Data from subjects' urodynamic testing will be abstracted from the clinical chart if performed within the prior 12 months of the enrollment date. If no urodynamics testing is available then we will not collect this information for those subjects. Subjects will also be counseled on the possible need for clean intermittent self-catheterization (CISC) and instructions on how and when to perform CISC will be given in clinic. Subjects will be randomized the day of the scheduled procedure. Subjects will be blinded to which group they are assigned.

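### Does it matter that the protocol does not say whether the baseline OAB-q and diary come before or after the drug washout?

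*Combined protocol and SAP*

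**What the plan says.** The inclusion criteria (item 1) state that "Patients who are on medical therapy will stop the medical therapy for at least 2 weeks prior to botulinum toxin A treatment". The section Protocol in detail repeats the rule: "At enrollment, any subjects who are using medical therapy", including anticholinergics and β3 agonists, "will stop these therapies for at least 2 weeks prior to treatment". Both statements count back from treatment.

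The next sentence of that section is "Baseline clinical data including OAB-q and a 3 day bladder diary will be collected as well as clinical and demographic information". It has no day, window or drug status. The paragraph then covers counseling on self-catheterization, where "instructions on how and when to perform CISC will be given in clinic", and ends with allocation: "Subjects will be randomized the day of the scheduled procedure". The 12-week diary, by contrast, is dated to the week before its visit.

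The primary outcome is the 12-week change from baseline in OAB-q bother. Diary incontinence episodes, diary voids and OAB-q quality of life are also changes from baseline. The null hypothesis is between-arm: "hydrodistention at the time of intradetrusor injection of botulinum toxin A will result in no difference in OAB-q score" compared with injection alone.

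**The concern.** Baseline is the reference value for the primary outcome and for three of the secondary outcomes. If a drug is holding symptoms down when the baseline OAB-q is completed, stopping it raises bother before the study treatment acts. That woman's recorded improvement is then understated by the size of the withdrawal effect. A woman who completes the form after the washout, or who takes no such drug, has no such deduction. Change from baseline would then mean different things for different women, and the mixture would add variance to the change score. The secondary aim of "24 week subjective improvement using the OAB-q" would have the same ambiguity if it is read against baseline.

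Only two contacts before treatment are described, enrollment and procedure day, so staff in the two recruiting clinics could follow the text faithfully and still time the forms differently. Three things could be at stake: bias in the arm comparison, power, and the meaning of within-arm improvement.

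**Working it through.** **1. What the text leaves open.** Protocol in detail runs in time order: consent, drug stop at enrollment, baseline forms, counseling, randomization on procedure day. Read that way, the forms are completed at or after the instruction to stop. A 3-day diary started then is just-stopped or drug-free, not fully on-drug. The main uncertainty is the OAB-q of women using drugs at enrollment. Women not using them are unaffected.

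**2. The plan's own figure.** Inputs from Power analysis: difference 15, SD of change 19, significance level 0.05 (taken as two-sided), power 80%. The two-sample t-test solution is 26.18 per arm, rounded up to 27, as stated. Power at 27 per arm is 81.2%. Allowing for dropout, 27 / 0.90 = 30 per arm, 60 in total, also as stated.

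**3. Bias.** Let p be the share on drug at baseline, d the rise in bother on stopping, and M1 and M2 the true mean improvements from a drug-free baseline. With on-drug baselines for all users, the expected recorded improvements are M1 − pd and M2 − pd, because p and d relate to a time before randomization. The difference is (M1 − pd) − (M2 − pd) = M1 − M2. A simulation of 200,000 trials at p = 0.5 and d = 10 gave a mean arm difference of 15.00 for a true 15.

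**4. Precision.** The documents give neither p nor d, and Data analysis names no test for the primary outcome. The following assumes a t-test on change scores, a true SD of 19 from a drug-free baseline, and all users on drug at baseline (the extreme case). Then SD = √(19² + p(1−p)d²).

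| p | d | SD | Power, 27 per arm |
|---|---|---|---|
| none on drug | – | 19.00 | 81.2% |
| 0.1 | 5 | 19.06 | 81.0% |
| 0.5 | 5 | 19.16 | 80.6% |
| 0.1 | 10 | 19.24 | 80.3% |
| 0.5 | 10 | 19.65 | 78.6% |

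For example, √(361 + 0.25 × 100) = √386 = 19.65. For a given d, p = 0.5 is the worst case, since p(1−p) is largest there.

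**5. Direction.** Suppose drug users also improve by e points more than non-users from their drug-free level. The SD is then √(361 + p(1−p)(e−d)²) with an on-drug baseline and √(361 + p(1−p)e²) with a drug-free one. The two are equal at e = d/2. At p = 0.5 and d = 10:

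| e | On-drug baseline | Drug-free baseline |
|---|---|---|
| 0 | 78.6% | 81.2% |
| 5 | 80.6% | 80.6% |
| 10 | 81.2% | 78.6% |

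**6. Cost of moving the forms to the end of the washout.** No visit is described between enrollment and the procedure, so the forms would be completed at home or, for the OAB-q, on the day itself. A baseline not obtained before the procedure is lost. If no one else drops out, one loss per arm takes 30 to 29 and power from 85.2% to 84.0%. If the three-per-arm allowance is already used, it takes 27 to 26 and power from 81.2% to 79.7%. Either loss (1.2 or 1.5 points) exceeds the largest effect in step 4 at d = 5, which is 0.7 points before rounding (81.24% to 80.58%).

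**The case for a change.** The best argument for acting is that the gap is real and cheap to close. No section supplies the timing, although the protocol dates the 12-week diary with care. Larger withdrawal effects would also cost more: at p = 0.5, power is 75.4% for d = 15 and 71.2% for d = 20. Within-arm improvement would be understated by pd, which is 5 points at p = 0.5 and d = 10. If dates were not kept, the mixture could not be sorted out later.

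Part of this stands. The omission is genuine, and within-arm changes need a note on when baseline was taken. The rest is weaker. Effects of 15 to 20 points equal or exceed the whole target difference, in women who qualify because drug therapy failed or was not tolerated. That makes a large effect less plausible, although the documents give no value. The shift of pd is common to both arms and does not bear on the null hypothesis. The protocol's silence on form fields does not show that dates go unrecorded, since the data collection sheets are not part of the document.

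**Conclusion.** No change to the plan follows. The protocol does not time the baseline OAB-q and diary against the drug stop, but this is missing detail that the study team can settle in conduct and describe in the report. With allocation on procedure day and baseline collected before it, the arm comparison is unbiased whichever timing was used. In the extreme case of every user being on drug at baseline, the loss at 27 per arm is 0.2 to 0.7 points of power for d = 5 and 1.0 to 2.6 points for d = 10 (p from 0.1 to 0.5, e = 0). The sign reverses once e exceeds d/2.

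These sizes rest on assumed p, d and e, on a t-test on change scores, and on the planning SD of 19 describing drug-free baselines. The documents do not settle whether that SD already includes mixed drug status. Requiring a post-washout baseline would risk lost forms for an uncertain gain, and an enrollment baseline is equally defensible. A line giving the time point, the drug stop date and the form dates would help readers of the within-arm results, but the between-arm conclusion does not depend on it.

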units of intradetrusor botulinum toxin A. A primary endpoint of 12 weeks showed a significant decrease in daily episodes of UUI episodes in the botulinum toxin A group compared to placebo [6,7]. Another double-blind, double-placebo-controlled, randomized trial compared anticholinergic use versus botulinum toxin A which showed a decrease in the number of episodes of UUI in the active group without any significant difference between treatments [8]. In this trial, both groups showed no significant differences in improvement in quality of life, but only 13% of patients in the anticholinergic group and 27% in the botulinum toxin A group reported complete resolution of UUI episodes [8]. Thus, we believe there is much room for improvement in the treatment of OAB symptoms.

Hydrodistention has been a treatment modality for interstitial cystitis (IC) since the early 1900s [9, 10]. It is thought that any efficacy for the treatment of IC is probably related to damage to mucosal afferent nerve endings in the bladder [11]. There are very limited studies on the use of hydrodistention for urgency and OAB symptoms. Dunn et al in a small study found that 14 of 20 patients with urgency and UUI reported resolution of their symptoms after prolonged bladder distention [12]. They also found that the bladder capacity in all patients increased after hydrodistention. In a retrospective review of patients undergoing hydrodistention, Cole et al found that in patients who had undergone the procedure for frequency and urgency symptoms with no pain component, 50% at 1 month, 19% at 3 months, and 7% at 6 months reported improvement in symptoms [13]. Other studies have shown no benefit from hydrodistention in the treatment of urgency and OAB symptoms [14, 15].

There are currently no studies investigating hydrodistention at the time of intradetrusor botulinum toxin A in patients with refractory OAB symptoms. We believe that patients may have additive benefit from a hydrodistention performed with botulinum toxin A injection as the

increased bladder capacity gained by the distention will be sustained for a longer period of time in the setting of botulinum toxin A.

Significance

No studies have been performed examining hydrodistention in the setting of intradetrusor botulinum toxin A for the treatment of refractory OAB symptoms.

Study Design

Inclusion criteria

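### Retention and infection are compared by arm, but the protocol specifies no collection of operative complications, bleeding, pain or unplanned care, so the risk side of adding hydrodistention is incomplete

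*Combined protocol and SAP*

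**What the plan says.** Under Intervention, both arms receive the same botulinum toxin A injection; the hydrodistention arm first has the bladder distended. Under Protocol in detail, two measurements are named for that added step. The volume from the first emptying is "recorded as initial bladder volume". After the 5-minute hold, "Upon emptying, the volume will be recorded as the hydrodistention volume". No procedure data item is named for the other arm.

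Three of the nine items under Secondary outcomes bear on safety, and all three apply to both arms:

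- Catheterization: "Proportion of subjects requiring clean intermittent self-catheterization (CISC) post-operatively as reported at 2 week post-operative visit". Protocol in detail adds the duration: "It will be recorded if subjects have had to use CISC including how many days".
- Residual volume: "Post-void residual volume (PVR) at the 2 week follow-up visit measured with catheter or bladder scan".
- Urinary tract infection: a positive culture in a woman with symptoms at the 2-week visit. Women who telephone with symptoms at any time and cannot give a culture are also treated and reported as infected. The listed symptoms include dysuria and suprapubic pain.

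The other six items are diary counts, questionnaires and ratings. At 6 and 12 weeks the text names the OAB-q, the global impression and the satisfaction questionnaire, with a diary before the 12-week visit. At 24 weeks it names the OAB-q alone.

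**The concern.** A trial of an added procedural step should describe the harms that the step might plausibly add. Here the plan covers voiding difficulty and infection and stops there. Operative bladder injury, bleeding, visible blood in urine afterwards, new bladder or pelvic pain, and unplanned visits or admissions have no place among the outcomes or the named visit data. There is also no general adverse-event section that would pick them up.

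Three things make this more than a missing detail. First, Background and Significance say that no study has examined this combination, so the protocol points to no other comparative harm data. Second, Background describes mixed evidence of benefit: improvement in 50%, 19% and 7% at 1, 3 and 6 months in one retrospective review, and no benefit in other studies. When benefit is uncertain, a decision to adopt leans more on harm. Third, symptoms that nobody asked about at the visit cannot be recovered at analysis.

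The infection definition adds a second problem. Discomfort caused by the distention, reported by telephone without a culture, would be counted as an infection. The harm would then appear under the wrong label, and the infection rate in the hydrodistention arm could be inflated.

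**Working it through.** **1. What is collected, set against the harms in question**

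| Harm | Where it appears | Reported by arm? |
|---|---|---|
| Retention | Secondary outcomes 3 and 4 | Yes |
| Urinary tract infection | Secondary outcome 5 | Yes, with uncultured calls included |
| Bladder injury or other operative complication | Nowhere | No |
| Bleeding, visible blood in urine | Unevaluated hematuria, as an exclusion criterion only | No |
| Bladder or pelvic pain | Suprapubic pain as an infection symptom; chronic pelvic pain as an exclusion | No |
| Unplanned visit or admission | Nowhere | No |
| Any other adverse event | Nowhere | No |

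**2. The plan's own sample size**

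Inputs from Power analysis: difference 15, standard deviation 19, level 0.05 (two-sided assumed, since the plan does not say), power 80%.

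- Normal approximation: n = 2 × (1.960 + 0.842)² × 19² / 15² = 25.2, so 26 per group.
- Two-sample t-test: 26.18, so 27 per group, with power 81.2% at 27.
- Dropout: 27 / 0.90 = 30 per group, 60 in total.

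The stated figures reproduce. They do not bear on harms, but they fix how many women would supply harm data: 30 per arm at operation, and about 27 at follow-up after 10% dropout.

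**3. What harm data from one arm could show**

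The documents give no rates for these harms, so the true rates p below are assumptions. The chance of seeing at least one event is 1 − (1 − p)ⁿ.

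| True rate p | n = 30 | n = 27 |
|---|---|---|
| 1% | 26% | 24% |
| 2% | 45% | 42% |
| 5% | 79% | 75% |
| 10% | 96% | 94% |

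If no event is seen, the one-sided 95% upper bound is 1 − 0.05^(1/n): 9.5% for n = 30 and 10.5% for n = 27. The two-sided 95% version for n = 30 is 1 − 0.025^(1/30) = 11.6%.

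**4. What a comparison between arms could show**

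Power at 30 per arm, two-sided 0.05, again under assumed rates:

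| Rates compared | Fisher's exact test | Normal approximation |
|---|---|---|
| 5% vs 15% | 9% | 25% |
| 10% vs 30% | 37% | 49% |
| 20% vs 40% | 30% | 39% |

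The same limits apply to the catheterization and infection comparisons already planned. Any added safety data would be descriptive.

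**The case against.** **Risk is already measured.** A reader might infer that the trial can report the benefit of hydrodistention but not its risk. The documents do not support that. Catheterization, residual volume and infection are outcomes in both randomized arms, and because hydrodistention is the only planned difference, a difference in any of them estimates added risk. This objection stands: the risk side is incomplete, not absent.

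**The rationale does not predict injury.** A reader might also take Background to say that hydrodistention is expected to work here by damaging the bladder. The sentence says that "any efficacy for the treatment of IC is probably related to damage to mucosal afferent nerve endings in the bladder", which concerns interstitial cystitis, an excluded condition. The rationale given for this trial is a longer-lasting gain in bladder capacity. This stands too, and the point does not rest on that sentence.

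**Forms may exist that the reader cannot see.** Confidentiality mentions data collection sheets, which are not in the document, and consent pages were removed. It would therefore be wrong to say that nothing is recorded. What can be said is that the protocol specifies none of these items. Neither risk disclosure nor institutional reporting would amount to a planned tabulation by arm.

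**The trial is too small for harms to be informative.** This is partly right, as the power figures show. It argues for calling the data descriptive. It does not argue for leaving them uncollected: a harm with a true rate of 10% would very probably be seen at least once, and the women are blinded, so their reports of blood or pain can be compared without knowledge of arm.

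**Conclusion.** The gap is real and cheap to close. The protocol compares retention and infection by arm but specifies no collection of operative complications, bleeding or visible hematuria, new pain or unplanned care, and no general adverse-event collection. Counting uncultured symptom calls as infection could also hide discomfort caused by the distention.

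The validity of the primary analysis is not affected. The consequence is that conclusions about the added step would rest on a partial account of its harms.

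A reader might hope that the added items would let a trial with no observed events call hydrodistention harmless. They would not: zero events among 30 women leaves rates up to 9.5% compatible with the data (one-sided 95%), or about 10.5% among 27. Common harms can be bounded; rare harms and modest differences between arms cannot. The bounds assume complete reporting in the stated number of women. The event rates used to illustrate detection are assumptions.

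**What to change.** Add a descriptive secondary safety outcome, collected the same way in both arms:

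- **Operative form:** bladder injury (yes/no) and bleeding needing intervention (yes/no).
- **Existing 2- and 6-week visits:** three fixed yes/no questions put to the blinded woman, on visible blood in urine, new bladder or pelvic pain, and any unplanned visit, emergency attendance or admission since the procedure.

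Report counts by arm with exact confidence intervals. Report culture-positive infection separately from uncultured symptom calls. In the hydrodistention arm only, record whether the 5-minute hold was completed. That is a measure of intervention fidelity; it has no counterpart in the other arm and does not belong in the safety comparison.

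The cost is three tick boxes on the operative form (the third in one arm only), three questions at visits already scheduled, and one extra line in the infection table. No visit or test is added, and the total stays at 60. The downside is a few more descriptive outcomes with wide intervals.
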